8.8.4	The percent of subjects with both acetabular cup abduction angle within +/- 10
	degrees of plan and acetabular cup version angle within +/- 10 degrees of plan will
	be summarized for both treatments and combined17
8.8.5	Harris Hip Score at Pre-Op, 6 week, 24 week
8.8.6	Forgotten Joint Score (FJS-12) at 6 week, and 24 week
8.8.7	EQ-5D-5L at Pre-op, Week 6, and Week2418

8.8.8	Hip Evaluation at Pre-op, 6 week, 24 week
8.8.9	Hip Evaluation Functional Recovery Outcomes19
8.8.10	Radiographic Outcomes (based upon: AP Hip, AP Pelvis, and Lateral) at week 6,
	week 24
8.8.11	Narcotic Drug Usage
8.9	Safety Analyses
8.10	Plans for Interim Analysis
8.11	Handling of Missing Data21
8.12	Adjustment for Multiplicity
8.13	Sensitivity Analyses
8.14	Subgroup Analysis
8.15	Assessment of Site Homogeneity
9	Data Monitoring Committee (DMC)21
10	Changes from the Study Protocol
11	Appendix A – Questionnaire Scoring
11.1	Harris HIP Score
11.1.1	HHS Scoring
11.2	Forgotten Joint Score (FJS-12)
11.2.1	FJS-12 Scoring
12	References
13	Tables, Listings and Graphs Shells

1 Study Design

This study is designed as a Prospective, Randomized, Multi-center Post-Market study of Anterior Advantage Surgical Approach in Total Hip Arthroplasty with and without the KINCISE[™] Surgical Automated System.

The primary objective of this study is to demonstrate that the mean femoral broaching time with KINCISE[™] is non-inferior to the mean femoral broaching time with manual instruments when used in THA with Anterior Advantage. If non-inferiority is successfully demonstrated then the study will be deemed successful, and a test for superiority for mean femoral broaching time will be conducted.

2 Treatment Assignment

After the subject is consented, it must be verified that the subject meets all eligibility criteria. Once confirmed, the subject will receive a planned treatment assignment, 'KINCISE' or 'MALLET', as described in section 3.

The treatment received, the actual treatment, will be recorded in the Operative eCRF and will be the basis for all safety and per-protocol analyses. If it is recorded on the Operative eCRF that KINCISE was used at any time during the study for femoral broaching and/or stem impaction then the treatment received will be KINCISE. If KINCISE was neither used for femoral broaching nor for stem impaction and if a mallet was used then the treatment received will be MALLET.

3 Randomization and Blinding Procedures

Sticker sheets were created, one set for up to 30 sites, containing treatment assignments for 120 subjects using a fixed block size of 4 and a treatment allocation ratio of 1:1. On the face of each sticker is a character in the sequence A, B, C,, X, Y, Z, AA, AB, AC,AX, AY, AZ, BA, BB, BC, etc...., BX, BY, BZ, CA, etc...

The stickers should be removed sequentially to reveal the randomization code and treatment group ('Study (Kincise)' or 'Control (Mallet)') for each consecutive consented subject that meets eligibility criteria. Peeled sticker should be placed on the screening log to document that randomization was unbiased. The planned randomization group should then be documented in the applicable source document and on the Randomization eCRF (eCRF RDM) in the database.

The assigned treatment will remain secret to site personnel until subject is found to meet all eligibility criteria; No other blinding is implemented in this study.

4 Interval Windows

The study includes the following periods: Pre-op, Operative, Immediate post-op, 6 Week, 24 Week. Intervals related to each are shown in Table 3, below.

Visit	Minimum Day	Maximum Day	Midpoint Day
Pre-Op	-180	0	
Operative	0	0	0
Immediate post-op	0	Discharge	
6 week	14	60	37
24 week	61	200	130

 Table 3
 Interval Windows for Non-Radiographic Study Visits

Time point specific data collected to satisfy the primary and secondary efficacy-related objectives will be assessed for compliance with these intervals. Only data which can be attributed to the visit intervals in Table 3 will be used in the analysis of primary and secondary endpoints. This visit will be hereafter referred to as the Analysis Visit and the originally recorded visit as the Nominal Visit. If multiple measurements fall into the pre-operative window, or into the 'Immediate post-op' post-operative window, the result collected most proximate to surgery will be utilized. For the '6 week' and '24 week' visits, if multiple measurements fall into the window will be utilized for analysis.

5 Levels of Significance

The level of significance is 95%. Primary endpoint analyses, further described in section 8.7, and secondary endpoint analyses with hypotheses, further described in 8.8, will use 1-sided 95% confidence intervals and associated p-values. Data summaries of secondary endpoints without hypotheses and of exploratory endpoints will use 2-sided 95% confidence intervals and associated p-values.

6 Analysis Sets

The following analysis sets are defined:

- Enrolled The Enrolled population set will consist of all subjects who sign the informed consent document.
- Safety The Safety population set will consist of all subjects in the Enrolled population set for whom treatment was attempted, according to the actual treatment received.
- Per Protocol The Per Protocol population set will consist of all subjects in the Enrolled population set who successfully received the planned treatment, who met all inclusion/exclusion criteria, who were seen at least once at a post-operative visit, and who did not have any protocol deviations which were prospectively determined to potentially have influence on the scientific validity of the data (such as inclusion/exclusion criteria).

7 Sample Size Justification

Primary endpoint Non-Inferiority (NI) analysis: Based upon input from key opinion leaders (KOLs) and data from other studies, typical femoral broaching time with manual instruments is anticipated to have a range of 5 to 15 minutes, which implies a standard deviation of approximately 2.5 minutes (1/4 of the range). Moreover, KOLs suggest that a difference of 10 minutes in femoral broaching time (increase for a single patient) is clinically meaningful. The non-inferiority margin of 1.25 minutes was established because it Page 8 of 29

is ½ of the anticipated standard deviation and is much less than a clinically meaningful difference. Under a 1-sided test with 5% alpha, a sample size of N=88 per group would be sufficient to demonstrate non-inferiority with 95% power. A sample of size N=200 per group (N=400 total) was chosen as feasible by the sponsor and desirable for providing further data for both KINCISE and Anterior Advantage; this sample size would provide more than 99% power to demonstrate non-inferiority for the primary endpoint analysis.

Primary endpoint supplemental superiority analysis: It is not known if there will be a true difference in means between groups. However, if there is a true difference of 1 minute between group means (lower time favoring KINCISE), and assuming an SD as stated above (2.5 minutes), then a sample of N=200 per group (N=400 total) would provide approximately 99% power to demonstrate superiority.

Secondary endpoint analyses:

• Non-inferiority of skin-to-skin OR time

Based upon input from KOLs and data from other studies, skin-to-skin OR time is anticipated to have a typical range from 60 to 90 minutes, which implies a standard deviation of approximately 7.5 minutes (1/4 of the range). The non-inferiority margin of 3.75 minutes was established because it is ½ of the anticipated standard deviation and is much less than the 10 minute clinically meaningful difference in femoral broaching time (a subset of skin-to-skin OR time). Under a 1-sided test with 5% alpha, a sample size of N=200 per group would be sufficient to demonstrate non-inferiority with greater than 99% power.

• Non-inferiority of optimal acetabular cup abduction

The percent of subjects within +/- 10 degrees of planned cup abduction for an anterior approach (AA) is anticipated to be between 90% and 95% (based on studies presented by Hamilton¹ and Rathod², respectively). These are a clinical improvement from percentages exhibited with a posterior approach (PA), which were 79% and 86% in [1] and [2], respectively. A NI margin of 10% was chosen because it is less than the improvement from PA to AA observed by Hamilton¹ and

Rathod². With this margin and a 1-sided test with 5% alpha, a sample size of N=200 per group would be sufficient to demonstrate non-inferiority with approximately 95% power.

• Non-inferiority of optimal acetabular cup abduction

The percent of subjects within +/- 10 degrees of planned cup version for an anterior approach (AA) is anticipated to be between 91% and 92% (based on studies by Rathod² and Hamilton¹, respectively). These are a clinical improvement from percentages exhibited with a posterior approach (PA), which were 64% and 77% in [1] and [2], respectively. A NI margin of 10% was chosen because it is less than the improvement from PA to AA observed by Hamilton¹ and Rathod². With this margin and a 1-sided test with 5% alpha, a sample size of N=200 per group would be sufficient to demonstrate non-inferiority with approximately 95% power.

In summary, with a sample size of N=400 (200 with KINCISE; 200 without KINCISE), the anticipated overall likelihood of demonstrating the primary endpoint non-inferiority analysis, followed by the three stated secondary endpoint non-inferiority analyses in the specified gate-keeping order, is at least $(99\%)(99\%)(95\%)(95\%) \approx 88\%$.

8 Analyses to be Conducted

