3.4 Enrollment, Randomization & Subject Identification (ID) Number

A patient will be enrolled in the study after signing the Institutional Review Board (IRB) approved informed consent form.

Each enrolled patient will be assigned a unique Subject identification number by the database. The first two digits of the Subject number represent the site identification number, followed by a hyphen, and three digits representing the sequential identification (*e.g.*, Subject 10-001 is the first number assigned at site 10). The Subject's unique identifier assigned in EDC will be recorded on each page of the eCRF and other study-specific documentation relating to that Subject (e.g. CRF source documents, patient reported outcomes, etc.). Subject numbers will be assigned for all patients who consent to participate in the study.

After the subject is consented, it must be verified that the subject meets all eligibility criteria. Once confirmed, the subject will be randomized into a treatment group. The sponsor will provide stickers in numerical order for each site. The stickers should be removed in numerical order to reveal the randomization code and treatment group for each consecutive consented subject that meets eligibility criteria. The sticker should be placed on the screening log to document that randomization was unbiased. The planned randomization group should then be documented in the applicable source document and on the Randomization eCRF (eCRF RDM) in the database. The subject will be randomized to either the Control – Anterior Advantage *without* KINCISE or the STUDY – Anterior Advantage *with* KINCISE group.

The flowchart presented below in Figure 3-1 depicts the process flow for screening, enrollment and randomization for the study.

The Principal Investigator must document the Subject's participation in this study in the Subject's clinic and hospital notes. If the subject is randomized to KINCISE, the surgeon should use KINCISE for the femoral broaching and as much as possible throughout the study where a mallet would have typically been used. However, if the surgeon feels it is necessary to use a mallet (i.e. impaction of the cup). Each use of the mallet should be documented on the Operative Details eCRF and in the source documents. If the surgeon uses the mallet as described above, it would not be considered a protocol deviation as long as KINCISE was used for the femoral broaching and as much as possible (per the randomization

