10.2 Treatment Assignment

See section 3.4 for the assignment of planned treatment.

Treatment received is defined as KINCISE if the KINCISE device was used for femoral broaching, MALLET otherwise.

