8.2 Disposition of Study Subjects

Counts of the following categories of subjects by treatment and in total will be provided: All Enrolled dataset, Safety, major inclusion/exclusion protocol violations, Per Prototol, non inclusion/exclusion major protocol violations, deaths, withdrawals, study completion, ongoing in the study.

A subject accounting table using the Safety set will also be provided to account for the following at each follow-up interval:

- Treated: the count of subjects treated; This should not vary per visit;
- Not Yet Due: the count of subjects who do not have an evaluation at the visit (Harris Hip or Forgotten Joint) and who, based on date of surgery and date of data extract, are not yet in-window for the visit;
- Theoretical Due: the count of subjects treated and not counted in Not Yet Due;
- Death: the count of theoretical subjects who died after the start of the window and who do not have data (Harris Hip or Forgotten Joint) at the visit;
- Revision: the count of subjects theoretically due, without data at the visit, who were revised and withdrawn from the study;
- Not Yet Overdue: count of theoretical subjects within the evaluation time window;
 Do not count subjects who have data at the visit or subjects who are counted in
 Death or Revision;
- Expected: the count of subjects theoretically due who are not counted in Death, Revision, Not Yet Overdue;
- Actual data on file (records with a date): the count of subjects with a record with a date for each of the following endpoints: RSA measured subsidence, cup positioning at 6 weeks, Harris Hip, HOOS Jr., Forgotten Joint score, and Linear head penetration. A count of subjects with a record with a date in any of the listed

endpoints will also be provided and a follow-up rate will be calculated using the number of expected subjects in the interval as denominator;

- -
- Any data on file: the count of subjects with any record with a date for the endpoints listed in "Actual data on file"
- Follow-up rate calculated as 100*(Any data on file)/Expected

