8.6 Device Deficiencies and Protocol Deviations

Listings of device deficiencies and protocol deviations will be provided.

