8.7 Primary Endpoint and Associated Hypotheses

The primary endpoint analysis is to demonstrate that femoral broaching time (in minutes)

with KINCISE is non-inferior to femoral broaching time with manual instruments (not using KINCISE) under a non-inferiority margin of 1.25 minutes.

Hypotheses for this non-inferiority analysis are as follows:

- Null Hypothesis: $H_0: \mu_I \ge \mu_C + 1.25$
- Alternative Hypothesis: H_A : $\mu_I < \mu_C + 1.25$

where μ_I and μ_C are mean femoral broaching times with and without KINCISE, respectively, and 1.25 is the NI margin. The null hypothesis will be rejected and non-inferiority will be concluded if the 1-sided upper 95% confidence limit for the $\mu_I - \mu_C$ difference (based upon a 2-sample t-test) is less than 1.25. The study will be deemed to be successful if this analysis demonstrates non-inferiority of femoral broaching time.

If non-inferiority is successfully demonstrated, then a test for superiority will be conducted to assess if femoral broaching time with KINCISE is less than femoral broaching time without KINCISE with statistical significance (1-tailed t-test with 5% alpha).

The primary endpoint analysis and all associated hypotheses will be conducted on the Per Protocol Analysis Set.

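### SAP 2 and Protocol 10.2 define treatment received differently, the change is not logged, and the Per Protocol rules do not settle which hips it affects

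*SAP*

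**What the plan says.** Protocol 10.2: "Treatment received is defined as KINCISE if the KINCISE device was used for femoral broaching, MALLET otherwise".

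SAP 2: the received treatment is KINCISE if "KINCISE was used at any time during the study for femoral broaching and/or stem impaction then the treatment received will be KINCISE". It is MALLET only when KINCISE was used for neither step and a mallet was used. This classification "will be the basis for all safety and per-protocol analyses".

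SAP 10 says its Table 10.1 presents the substantive changes from the protocol. It has two rows, on thigh pain and on the wording of the gatekeeping rule. The definition of treatment received is not among them.

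The Per Protocol set (Protocol 10.6, SAP 6) requires that the planned treatment was successfully received. It also requires that there was no deviation of a kind fixed in advance as able to affect validity. Eligibility criteria are the only example given. SAP 8.2 plans a count of "non inclusion/exclusion major protocol violations", so other excluding deviations are expected, but neither document lists them.

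Protocol 3.4 requires KINCISE for broaching in the KINCISE arm and calls failure to do so a deviation. Mallet use at other steps in that arm is tolerated: "it would not be considered a protocol deviation as long as KINCISE was used for the femoral broaching". In the control arm the mallet is required at every step.

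The primary test (Protocol 10.5.1, SAP 8.7) compares "mean femoral broaching times with and without KINCISE, respectively". Protocol 4.1 ends the broaching clock when the final broach trial is seated, before the stem is impacted. The primary and the three gated secondary tests all use the Per Protocol set.

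**The concern.** A hip that was never broached with KINCISE has a mallet broaching time, whatever tool later drove the stem. Under the SAP rule such a hip in the KINCISE arm has received its planned treatment and can stay in the KINCISE mean. Under the protocol rule it has not, and it drops out. In the control arm the answers are reversed. The composition of the set behind every formal test therefore depends on which document is followed and on a list of excluding deviations that neither document contains.

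The trial is open after assignment (SAP 3: "No other blinding is implemented in this study"). If the list is not fixed in writing before analysis, membership could be settled with arm and broaching time in view. SAP 8.13 plans no sensitivity analysis that would show the result under the other rule.

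The Safety set is also affected. The same hip is counted under different treatments in the two documents, and the SAP rule leaves some hips with no treatment at all.

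**Working it through.** **Side-by-side classification**

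| Hip | Protocol 10.2 | SAP 2 |
|---|---|---|
| Any KINCISE broaching | KINCISE | KINCISE |
| Mallet broaching only, KINCISE stem impaction | MALLET | KINCISE |
| KINCISE for neither step, mallet used | MALLET | MALLET |
| KINCISE for neither step, no mallet (for example withdrawn before either tool was used) | MALLET | unclassified |

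Second row, through the planned-treatment clause alone:
- Randomised to KINCISE: out of Per Protocol under the protocol rule, in under the SAP rule.
- Randomised to mallet: in under the protocol rule, out under the SAP rule.

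The deviation clause could remove these hips in both arms, and the two Per Protocol sets would then agree on them. Neither document says whether it does.

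**The plan's own figures.** With margin 1.25, SD 2.5, one-sided 5% and true difference 0, the noncentral t gives 94.9% power at 87 per group and 95.1% at 88. At 200 per group it gives 99.96%. The stated 88 per group and more than 99% are reproduced.

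**Illustration of the SAP rule.** From the documents: SD 2.5, 200 per arm, margin 1.25. Assumed, because the documents give nothing: k such hips are retained in the KINCISE arm, and their mean is d minutes above the control mean. Let f = k/200, and let δ be the KINCISE-broached mean minus the control mean.

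- m = (1 − f)δ + f·d
- SE = √{[2.5² + f(1 − f)(d − δ)²]/200 + 2.5²/200}, about 0.25
- P(conclude non-inferiority) = Φ((1.25 − m)/SE − 1.645)

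At δ = 1.25 and d = 0, m is 1.2438, 1.2375, 1.225 and 1.1875 for k = 1, 2, 4 and 10. Type I error:

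| Retained hips average | k=1 | k=2 | k=4 | k=10 |
|---|---|---|---|---|
| control mean (d = 0) | 5.3% | 5.5% | 6.1% | 8.1% |
| 1.25 min above control | 5.0% | 5.0% | 5.0% | 5.0% |
| 2.5 min above control | 4.7% | 4.5% | 4.1% | 2.9% |

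The protocol rule gives 5.0% throughout. That is by construction: the null is set on KINCISE-broached hips, and the others are dropped without selection.

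**Scale of one hip.** Non-inferiority is concluded when the observed difference is below about 1.25 − 1.645 × 0.25 = 0.84 min. One hip lying 1.25 min from the KINCISE-broached mean moves the arm mean by 1.25/200 = 0.006 min.

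**Power.** At zero true difference with d = 0, m stays at 0 and non-inferiority power stays above 99.9%. For superiority with δ = −1 and d = 0:
- SAP rule, Φ(−m/SE − 1.645): 98.8% at k = 4 (m = −0.98) and 98.4% at k = 10 (m = −0.95).
- Protocol rule, with k hips dropped and SE = 2.5√(1/(200 − k) + 1/200): 99.0% and 98.9%.
- Gap between the rules: about 0.2 and 0.5 percentage points. With no such hips both give 99.1%.

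**The case against.** The best defence is that the conflict may never matter.

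- **The Per Protocol clauses may already exclude these hips.** Read with Protocol 3.4, the planned-treatment requirement could be taken to remove them in both arms. The excluding deviations are said to be fixed in advance and may be listed in a document not seen here. This reading is possible, but SAP 2 says its own definition governs the per-protocol analyses, and under that definition the KINCISE-arm hip did receive its planned treatment. The defence therefore rests on a list that neither document supplies.
- **The class may be empty.** The fallback example in Protocol 3.4 is mallet use for the cup after KINCISE broaching, and such a hip is KINCISE under both rules. This stands: nothing in the documents shows that any affected hip exists.
- **The SAP rule suits safety.** Counting any KINCISE broaching or stem impaction as exposure is defensible for the Safety set. This also stands. It does not carry over to an endpoint that is complete before the stem is impacted.
- **The hips can be found.** SAP 8.4 lists steps by tool, and SAP 8.6 says "Listings of device deficiencies and protocol deviations will be provided". This makes correction easy but does not say which rule applies.

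A reader might infer that the two rules would often give different non-inferiority conclusions near the 0.84 min cut. In simulation at a true difference of 0.84 min they disagreed in 1.9, 2.5, 4.0 and 8.2% of trials for k = 1, 2, 4 and 10 with d = 0. Removing the same number of hips that do not differ from other KINCISE hips gave 1.6, 2.1, 3.3 and 5.3%. At small k most of the disagreement comes from dropping any hips at all, so it should not be quoted as an effect of misclassification.

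**Conclusion.** The inconsistency is real and unlogged, and as written the SAP rule can place a mallet broaching time in the KINCISE mean. Severity is minor.

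The size is unknown because the documents give no count of such hips. The direction is undetermined because it depends on how long those hips took. The error rates above rest on the planning SD, 200 per arm, an assumed count and an assumed mean for the affected hips. They are not a forecast. The effect on the primary conclusion is negligible unless such hips exist, the deviation filter leaves them in, and the observed difference is close to 0.84 min.

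Two stronger readings are not supported. One is that the SAP definition inflates the type I error of the primary test: the error rises, stays at 5.0% or falls according to d. The other is that the protocol rule protects the randomised comparison: it also drops randomised hips on the basis of what happened in theatre. The reason to prefer it for this endpoint is only that it matches the means being tested and the compliance rule for the KINCISE arm in Protocol 3.4.

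**What to change.** Before analysis:

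1. In SAP 2, for the Per Protocol set and the broaching-time endpoint, use the Protocol 10.2 rule: KINCISE if it was used for any femoral broaching, MALLET otherwise.
2. In SAP 6, state whether the device-use breaches of Protocol 3.4 that bear on broaching or stem impaction exclude a subject from Per Protocol. There is no need to extend this to every KINCISE use in a control hip; that would go beyond reconciling the two definitions.
3. State one Safety grouping rule that classifies every treated hip, including those with neither tool used. The SAP exposure rule may stay for this purpose.
4. Add the definition to SAP Table 10.1 and report the number of affected hips by arm.

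A rerun of the primary test under the other rule is needed only if the breaches are not named as exclusions and such hips exist. If they are named, the rerun would repeat the same analysis.

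The cost is a few SAP sentences, one table row and one count. No new data are needed: steps by tool are planned listings (SAP 8.4), mallet use in the KINCISE arm goes on the Operative Details eCRF (Protocol 3.4), and KINCISE adapters go on the Device Log (Protocol 11).

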5.1 Study Design Summary

This is a post-market randomized, prospective, multi-center study with a planned analysis of 400 subjects (200 per treatment group). Up to 20 study sites will be approved to participate in this study. Each site is expected to enroll the number of subjects as outlined in their clinical trial agreement. It is anticipated that each site will enroll approximately 20 subjects per arm (40 subjects total). Reallocation of patients may occur to allow completion of study enrollment in a timely manner. Sites may replace Subjects that are screen failures and preoperative or intraoperative withdrawals to ensure adequate numbers for final analysis.

Competitive enrollment will be utilized and managed by the sponsor. The sponsor will communicate to each site regarding increased or decreased enrollment allotment and each site should anticipate enrolling 40 total subjects (20 per arm) unless it is communicated otherwise. Details regarding sample size are presented below in **Section 10.8**.

Each site will use the Pinnacle cup and the stem (Corail or Actis uncemented) that fit with their standard of care. The devices used in this study are available to all patients needing uncemented THA whether they choose to be a part of the study or not, since this is a post-market study.

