15.6 Clinical Investigation Plan (CIP) Amendments

Applicable IRB approvals will be obtained prior to implementation of changes in the Clinical Investigational Plan that may affect the scientific soundness of the investigation or the rights, safety or welfare of study subjects. Administrative changes must also be submitted to the reviewing IRB.

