8.8 Secondary Endpoints and Associated Hypotheses

All secondary endpoint analyses and associated hypotheses will be conducted on the Per Protocol Analysis Set.

If the primary endpoint analysis successfully demonstrates non-inferiority of femoral broaching time, regardless of whether the above test of superiority was successful or not, then the following three secondary endpoint analyses will be conducted under a gatekeeping strategy, in this specified order, where testing is performed in sequence and continues until a null hypothesis is not rejected or all hypotheses have been tested, each with a 1-sided alpha of 0.05:

- 8.8.1 Skin-to-skin OR time
 - Skin-to-skin OR time in minutes will be summarized as a continuous variable for both treatments and combined
 - A non-inferiority test of skin-to-skin OR time will be conducted with a noninferiority margin of 3.75 minutes, using a 2-sample t-test:
 - Null Hypothesis: $H_0: \mu_I \ge \mu_C + 3.75$
 - Alternative Hypothesis: H_A : $\mu_I < \mu_C + 3.75$
 - where μ_I and μ_c are mean skin-to-skin OR times with and without KINCISE, respectively. The null hypothesis will be rejected and non-inferiority will be concluded if the 1-sided upper 95% confidence limit for the μ_I μ_c difference (based upon a 2-sample t-test) is less than 3.75
 - The 1-sided upper 95% confidence limit for the difference and the pvalue will be presented.
- 8.8.2 The percent of subjets with acetabular cup abduction angle within +/- 10 degrees of plan
 - The proportion of subjets with acetabular cup abduction angle within +/- 10 degrees of plan will be summarized for both treatments and combined
 - A non-inferiority test of the percent of subjects with acetabular cup abduction angle within +/- 10 degrees of plan under a NI margin of 10% will be conducted:
 - Null Hypothesis: $H_0: P_I \le P_C 10\%$
 - Alternative Hypothesis: $H_A: P_I > P_C 10\%$
 - where P_I and P_c are the percentages of subjects with acetabular cup abduction angle within 10% of plan with and without KINCISE, respectively. The null hypothesis will be rejected and non-inferiority will be concluded if the 1-sided lower 95% confidence limit for the P_I –

 P_{C} difference (based upon a normal approximation method) is greater than -10%

- The 1-sided lower 95% confidence limit for the difference and the pvalue will be presented.
- 8.8.3 The percent of subjects with acetabular cup version angle within +/- 10 degrees of plan

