8.13 Sensitivity Analyses

No sensitivity analyses will be conducted.

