8.15 Assessment of Site Homogeneity

No formal assessment of site homogeneity will be conducted.

9 Data Monitoring Committee (DMC)

A DMC will not be used to monitor safety or efficacy in this study.

10 Changes from the Study Protocol

The basis of this Statistical Analysis Plan (SAP) is the Clinical Investigation Plan (CIP). Changes have been made to address any typographical errors and improve clarity and consistency of terminology. In addition, substantive changes are presented in the following table:

Content	Modification	Justification
Pain (Groin, Thigh,	Thigh pain is removed	Thigh pain data is not
and Buttock) as a		collected on the hip
secondary endpoint		evaluation CRF
Section 10.5.2 of the	"alternative" is replaced with	We continue testing endpoints
study protocol:	"null"	as long as the null is rejected.
"gatekeeping		We stop as soon as the null
strategy, in this		hypothesis is not rejected.
specified order,		
where testing is		
performed in		
sequence and		
continues until an		
alternative		
hypothesis is not		
rejected"		

Table 10.1Summary of Substantive Changes

11 Appendix A – Questionnaire Scoring

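### Randomisation is blocked within site, but both operating-time endpoints are tested with a t-test that ignores site, so the limits are somewhat too wide if sites differ

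*SAP*

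**What the plan says.** Protocol 3.4 states that "The sponsor will provide stickers in numerical order for each site". SAP section 3 gives the detail: "Sticker sheets were created, one set for up to 30 sites, containing treatment assignments for 120 subjects using a fixed block size of 4", at 1:1. The SAP wording alone could be misread as a single shared set. However, 120 assignments could not cover 400 subjects, and the protocol sentence settles that the lists are per site.

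The analysis does not use this structure. For broaching time, SAP 8.7 concludes non-inferiority if the one-sided upper 95% limit ("based upon a 2-sample t-test) is less than 1.25") meets the margin, followed by a one-tailed t-test for superiority. SAP 8.8.1 does the same for skin-to-skin time ("based upon a 2-sample t-test) is less than 3.75"). Protocol 10.5.1, 10.5.2, 10.9.3 and 10.9.4 match.

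SAP 8.13 says "No sensitivity analyses will be conducted" and SAP 8.15 says "No formal assessment of site homogeneity will be conducted". SAP 8.14 leaves room for post-hoc analyses, but nothing that accounts for site is pre-specified for either endpoint.

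**The concern.** When allocation is balanced within site, a site that is slow overall contributes equally to both arms, so its slowness cancels from the difference in means. The 2-sample t-test does not know this. It puts the between-site spread into its error variance and reports a standard error larger than the real sampling variation of the estimate. Confidence limits are then too wide, p-values too large, and precision that the design has already bought goes unused.

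The plan makes site differences plausible. Protocol 5.1 lets each site use the stem that fits its own practice. Protocol section 1 allows different operating tables, with or without intraoperative imaging. Protocol section 7 leaves operative procedure to the surgeon. All of these can cluster by site and affect operating time.

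The point concerns site only. Surgeon differences within a site are not blocked; for those the t-test is correctly calibrated and merely less precise.

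**Working it through.** **Inputs from the documents** (SAP section 7, protocol 10.8): one-sided alpha 0.05; 200 per group; broaching SD 2.5 min, margin 1.25 min; skin-to-skin SD 7.5 min, margin 3.75 min; superiority planned for a 1-min difference. The SDs are totals, not split into between- and within-site parts.

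**Assumed:** site ICC of 0.1, 0.2 or 0.3, with a treatment effect common to all sites. At ICC 0 nothing is lost.

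**Step 1: the plan's own figures reproduce.** Normal approximation: n = 2(1.645 + 1.645)² × 2.5² / 1.25² = 86.6, so 87. The noncentral t gives power 0.9495 at 87 and 0.9514 at 88, matching the stated 88. At 200 per group, non-inferiority power is 0.9996 for each time endpoint (stated: above 99%), and superiority power for 1 min is 0.991 (stated: about 99%).

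**Step 2: standard errors.**
- SE used by the t-test ≈ SD × √(2/200): 0.25 min for broaching, 0.75 min for skin-to-skin.
- True SE under site blocking = SD × √(2/200) × √(1 − ICC).
- Ratio = 1/√(1 − ICC).
- True one-sided alpha of the t-test = Φ(−1.645/√(1 − ICC)).
- Half-width = 1.645 × SE.
- Equivalent sample size = 200/(1 − ICC).
- Power = Φ((distance to the null boundary − 1.645 × SE used)/true SE); for the site model, SE used equals true SE.

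| | ICC 0.1 | ICC 0.2 | ICC 0.3 |
|---|---|---|---|
| SE too large by | 5% | 12% | 20% |
| True alpha of t-test | 4.1% | 3.3% | 2.5% |
| Broaching half-width, t-test vs site model (min) | 0.41 vs 0.39 | 0.41 vs 0.37 | 0.41 vs 0.34 |
| Skin-to-skin half-width (min) | 1.23 vs 1.17 | 1.23 vs 1.10 | 1.23 vs 1.03 |
| Superiority power, 1 min | 99.4 vs 99.5% | 99.6 vs 99.8% | 99.8 vs 99.9% |
| Superiority power, 0.5 min (assumed) | 65 vs 68% | 65 vs 72% | 66 vs 77% |
| Equivalent n per group with site model | 222 | 250 | 286 |

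Non-inferiority power at zero difference is at least 99.9% by either method for both endpoints. If KINCISE were truly 2 min slower skin-to-skin (assumed) at ICC 0.2, the distance to the margin is 1.75 min and the true SE is 0.75 × √0.8 = 0.671. Power is then 78% with the t-test and 83% with the site model.

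**Step 3: simulation.** Allocation in blocks of 4 within site, true difference at the 1.25 margin, rejection rate at ICC 0.1 / 0.2 / 0.3:
- 10 sites of 40 (20,000 replicates): t-test 4.1 / 3.5 / 2.6%; site model 4.8 / 5.2 / 4.8%.
- 20 sites of 20 (6,000): 4.2 / 3.4 / 2.4%; 4.8 / 5.1 / 5.0%.
- 20 unequal sites of 1 to 70 subjects (6,000): 3.9 / 3.7 / 2.7%; 4.7 / 5.1 / 4.7%.

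The Monte Carlo standard error at 6,000 replicates is about 0.3 percentage points (√(0.05 × 0.95/6000) = 0.0028). In a further run at ICC 0.2 (10 sites of 40), the t-test's mean SE was 0.247, the actual SD of the estimate 0.225, and the site-model SE 0.224. With 10% of subjects dropped at random, to mimic per-protocol exclusions, alpha was 3.9% unadjusted and 4.9% adjusted.

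**Step 4: where the common-effect condition fails.** If the true effect varies between sites (assumed SD 0.5 min, 10 sites, ICC 0.2) and inference is to a wider population of sites, two runs gave alpha of 6.2% and 6.8% for the t-test and 8.5% and 9.0% for the site model. At an effect SD of 1.0 min the figures were 13.3% and 16.0%. Neither method covers that target.

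**The case against.** The strongest reply is that the error runs in the safe direction and costs nothing the plan set out to achieve. SAP 8.12 promises a family-wise error no greater than 5%, and a conservative t-test keeps that promise. Planned powers are 99% or more either way. The ICC is assumed: at 0.05 the SE is only 2.6% too large and alpha about 4.6%. Even at 0.1 to 0.3 the half-width shrinks by roughly 1 to 4 seconds against a 75-second margin for broaching, and by 4 to 12 seconds against 225 seconds for skin-to-skin time. The visible gains come from effects the plan did not power for. If effects vary by site, the site model is further from 5% than the t-test.

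Most of this stands as fact, and it limits the point to one of efficiency and calibration. It does not make the t-test the better choice. The plan itself says the true difference is unknown, superiority is a planned test, and a result near a margin is where 12% of a standard error would count. If the ICC is zero, adjusting costs at most 19 of about 398 degrees of freedom with 20 sites. The site-varying case argues for stating the inference target and showing effects by site; the t-test does not hold 5% there either.

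Two further remarks are fair. The two cup-angle tests share the blocked design and could be stratified in the same way. Any cut-off for pooling small sites is a convention.

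**Conclusion.** The concern holds. Site is a randomisation stratum and no pre-specified analysis of either time endpoint uses it. If sites differ and the effect is common, the t-test's standard error is too large by 1/√(1 − ICC), which is 5 / 12 / 20% at ICC 0.1 / 0.2 / 0.3, and true one-sided alpha falls to about 4.1 / 3.3 / 2.5%. The size rests on an ICC that the documents do not give.

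This is a loss of precision, not a threat to validity or to the planned non-inferiority conclusions. It matters for superiority if the benefit is below 1 min (3 to 11 percentage points of power at 0.5 min), for results near a margin, and for reporting limits that match the randomisation. The change should be made because it is cheap and needs no data that the trial does not already hold.

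**What to change.** - Make the primary method for broaching time (non-inferiority and superiority) and skin-to-skin time a linear model with treatment and randomising site as a fixed factor. Take the one-sided 95% limit from the treatment contrast, and state that inference is to the participating sites.
- Pre-specify a small-site rule, since Protocol 5.1 says "Competitive enrollment will be utilized and managed by the sponsor" and some sites may stay small. One option is to pool sites with fewer than 8 analysed subjects (two blocks), or with only one arm represented, into a single stratum.
- Add a descriptive summary of the treatment difference by site, and keep the 2-sample t-test as supportive.
- Settle this before operative data are seen by arm. SAP 8.10 allows operative endpoints to be summarised after about 15 subjects per group.

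**Cost:** SAP 8.7 and 8.8.1 and protocol 10.5.1, 10.5.2, 10.9.3 and 10.9.4 must change together; SAP 8.13 and 8.15 should be brought into line. That means a short amendment with IRB submission; under Protocol 15.6, "Applicable IRB approvals will be obtained prior to implementation of changes". No new data are needed, because site is already part of the subject number (Protocol 3.4), and no extra patients are needed.
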